**Bazedoxifene/Conjugated Estrogens (BZA/CE)
Improvement of Metabolism**

NCT Number: NCT02237079

Protocol Date: 7/26/2017

Bazedoxifene/Conjugated Estrogens (BZA/CE) Improvement of Metabolism

1. Study aim, background, and design

With the dramatic increase in life expectancy, many women will spend half of their lives in a post-menopausal state of estrogen deficiency that increases risk for metabolic syndrome, type 2 diabetes (T2D) and non-alcoholic fatty liver diseases (NAFLD).¹ Overall, the role of estrogen deficiency to the pathophysiology of chronic metabolic diseases in women is emerging as a novel therapeutic challenge. In 1995, approximately 38% of postmenopausal women in the U.S. used **hormone therapy (HT)**, consisting of estrogen with or without progestin, to treat symptoms of menopause and to prevent chronic conditions such as cardiovascular disease (CVD) osteoporosis, and Alzheimer's.² It was not until the Women's Health Initiative (WHI) was abruptly halted in 2002 as a result of a link between HT and increased risk of coronary heart disease events, stroke and breast cancer that the health benefits of HT were seriously questioned.³ Results of the WHI led many women and their physicians to overestimate the individual-level risk associated with HT use. Fortunately, the period after 2010 saw a detailed analysis of the WHI and led to a stratification of the absolute risk of HT by age. Recently, the benefits of estrogen therapy have been reevaluated by international menopausal societies leading to a consensus on the benefits of HT pending that it is administered in early menopausal women and is not associated with a progestin.⁴ The most promising HT involves the use of tissue selective estrogen complexes (TSECs) combining a conjugated estrogen (CE) and the selective estrogen receptor modulator (SERM) bazedoxifene (BZA) in a single tablet. The major innovation of TSEC BZA/CE is that it provides all the advantages of CE treatment without the use and side effects of a progestin.^{5,6} Another advantage is that it contains BZA, a SERM that has estrogen antagonistic activity in breast and uterus and estrogen agonistic activity in bone thus preventing osteoporosis while protecting the breast and uterus from estrogenic stimulation.⁶ BZA/CE (DUAVEE) is this novel menopausal therapy approved by the FDA for the treatment of postmenopausal symptoms and the prevention of menopausal osteoporosis. However, an important beneficial effect of estrogen is also to prevent postmenopausal metabolic disorders.^{1,7,8} There is currently no information on the efficacy of BZA/CE in preventing postmenopausal metabolic disorders. Our recent preliminary data, derived from a mouse model of post-menopausal metabolic syndrome, demonstrate that the combination BZA/CE prevent estrogen deficiency-induced metabolic dysfunction-including obesity, T2D and NAFLD- and without uterus stimulation.⁹ Because SERMs like tamoxifen or Raloxifene have never shown such a beneficial metabolic effect in preclinical models and in humans,¹ these data underscore the clinical significance of this line of investigation and they also provide a firm rationale for proposing a pilot study to assess the efficacy of BZA/CE in preventing metabolic dysfunction in postmenopausal women.

The goal of this pilot clinical study is to perform a **randomized placebo-controlled study** to assess the beneficial effect of a **3 month-treatment** with BZA/CE vs. *placebo* on glucose homeostasis and body composition in 30 post-menopausal women. The recruitment will be performed at Tulane Health Sciences Center. The following endpoint will be measured ***at the beginning of the study and after 3 months of treatment***. Patients will have a monthly visit with the clinical coordinator.

a) ***Effect of DUAVEE™ on visceral adiposity. Rationale:*** Our preliminary data show that TSEC treatment prevents visceral fat accumulation in ovariectomized female mice with diet-induced metabolic dysfunction.⁹ It also decreases hepatic and skeletal muscle triglyceride accumulation⁹ in these ovariectomized mice. ***Hypothesis:*** BZA/CE will improve visceral obesity in postmenopausal women. ***Design:*** We will determine the effect of a 3 month- treatment with DUAVEE on body mass index (BMI), waist to hip circumference (WHR)-a clinical index of visceral fat accumulation- and

Version Date: 07/26/17

Version Number: 9.0

Page 2 of 17

directly quantify abdominal fat by DEXA Scan. **We expect** that BZA/CE treatment will improve WHR and decrease abdominal fat in postmenopausal women.

b) ***Effect of BZA/CE on glucose homeostasis. Rationale.*** Our preliminary data shows that TSEC treatment decreases fasting and fed blood glucose levels (as a result of improved insulin sensitivity) in ovariectomized female mice with diet-induced metabolic dysfunction.⁹ **Hypothesis:** DUAVEE™ treatment will decrease glucose and insulin levels in postmenopausal women. **Design:** We will determine the effect of a 3 month- treatment with DUAVEE on fasting and fed glucose and insulin levels. **We expect** that BZA/CE treatment will decrease glucose and insulin levels in postmenopausal women.

c) ***Clinical modelization of the impact of BZA/CE on glucose homeostasis. Rationale.*** Our preliminary data shows that TSEC treatment improves insulin resistance and glucose tolerance in ovariectomized female mice with diet-induced metabolic dysfunction.⁹ **Hypothesis:** DUAVEE treatment will ameliorate insulin sensitivity and glucose tolerance in postmenopausal women. **Design:** We will determine the effect of a 3 month- treatment with DUAVEE™ on glucose homeostasis following an IV-Glucose Tolerance Test (IVGTT) which will be studied using the minimal model. In the minimal model, computer software is used to calculate insulin sensitivity and secretion from the glucose and insulin dynamics observed during the IVGTT.¹⁰⁻¹² Three major independent parameters can be derived: *The insulin sensitivity index (S)* is the measure of the capability for insulin-stimulated glucose uptake; *the acute insulin response to glucose (AIRg)* which is the total insulin release during the first phase of insulin secretion and *the disposition index (DI)* which is the ability of an individual to control blood glucose taking into consideration insulin secretion in the face of the prevailing degree of insulin resistance.¹³ Therefore, the DI a major therapeutic index when assessing a new drug. The IVGTT coupled to the minimal model is the gold standard and provides the most clinically relevant comprehensive metabolic portrait of an individual.¹⁰ **We expect** that BZA/CE treatment will enhance insulin sensitivity (S) and the disposition index (DI) in postmenopausal women.

d) ***Effect of DUAVEE™ on systemic inflammation. Rationale.*** Our preliminary data show that TSEC treatment improves systemic markers of inflammation and metabolic dysfunction in ovariectomized female mice with diet-induced metabolic dysfunction. Metabolic dysfunction is characterized by recruitment and release of pro-inflammatory cytokines from WAT that cause insulin resistance and a general, low-grade systemic inflammatory state. Our preliminary data show that serum leptin levels and the leptin/adiponectin ratio — a marker of insulin resistance and atherosclerosis — were markedly decreased by TSEC treatment in ovariectomized female mice fed a HFD.⁹ In addition, TSEC treatment decreased serum levels of RBP4, an adipokine that is elevated in insulin resistance and type 2 diabetes.⁹ Further, TSEC treatment reduced serum levels of Lcn2,⁹ an adipokine that is also elevated in adipose tissue and in serum of obese and insulin resistant rodents and humans. Finally, serum levels of TBARS, a marker of oxidative stress and lipid peroxidation, were significantly decreased in OVX mice by TSEC treatment.⁹ Thus, in ovariectomized female mice fed a HFD, TSEC improves adipose dysfunction and systemic inflammation and protect against lipid peroxidation and oxidative stress. **Hypothesis:** BZA/CE treatment will improve systemic markers of inflammation in postmenopausal women. **Design:** We will determine the effect of a 3 month- treatment with DUAVEE on serum cytokines measurement (Leptin - Insulin - adiponectin - RBP4 - LCN2 - TNF α - IL6 - PAI-1 - FGF21). **We expect** that BZA/CE treatment will improve systemic markers of inflammation, lipid peroxidation and oxidative stress in postmenopausal women.

Study Duration: Duration of the recruitment + treatment of patients: 1 year

Target Start and End Dates: October, 2014 – September, 2015.

Predicted outcome: We can foresee two possible outcomes. The most likely is that a 3 month-treatment with BZA/CE in postmenopausal women decreases visceral adiposity and markers of systemic inflammation and improves insulin resistance and glucose homeostasis. There are several reasons to anticipate these positive results. *First*, CE is already known to improve glucose and energy homeostasis in postmenopausal women¹ and should continue to have the same activity in a TSEC. *Second*, an importantly SERMs like tamoxifen or raloxifene have never shown any beneficial metabolic effect in rodents and humans.¹ Conversely, BZA exhibits a powerful metabolic effect in female mice and accordingly, we expect that it will translate to women. Finally, TSEC shows a beneficial effect on HFD-induced obesity, independently from estrogen deficiency in mice, suggesting that it may also improve obesity in women. For all these reasons, we are confident that BZA/CE anti-diabetic and anti-obesity effects will translate to postmenopausal women. Acquisition of this information is critical to open novel avenues of therapies for postmenopausal women. The second possible outcome is that although our data generated in pre-clinical models are quite convincing and strongly suggests that BZA/CE will improve metabolic health in women, our hypothesis may not prove correct. This pilot study needs however to be performed because if successful, such preliminary data can lead to new therapeutic avenue for post-menopausal metabolic disturbances.

Statistical Methods: According to our preliminary data obtained in mice,⁹ TSEC treatment increased whole body glucose disposal by 30% and enhanced hepatic insulin sensitivity by 75% compared to vehicle. Although a formal power analysis was not feasible in the pilot study, in light of the high precision that is achieved using the minimal model, we can expect similar improvements to be detectable with 30 patients for whole body insulin sensitivity (Si and DI) in this randomized trial. Our statistician will conduct our data analysis. Briefly, a mixed effects statistical model will be used to investigate the within subject differential response to BZA/CE compared to placebo. Statistical significance will be set at $p < 0.05$. Analysis will be carried out using the software package SAS V 9.3, SAS Institute, Inc. Cary, NC.

2. Subject Population

We will recruit and screened participants with the aim of randomizing 30 women (10 per group). After referral and clearance (see below), the final assessment of eligibility will be performed during a **screening visit** (blood, medical history and physical examination, barriers to participation, questionnaires). Breast exam and/or mammography will be part of the screening to assess eligibility.

Inclusion:

- Post-menopausal women (<5y since final menstrual period) with age between 50-60y
- Symptomatic (hot flashes, vaginal dryness) or asymptomatic
- BMI 26-45 kg/m² (Overweight, Obesity I and Obesity II)
- fasting glucose <125mg/dl
- Triglycerides < 200 mg/dl
- Normal mammogram within past 12 months
- Physician clearance

Version Date: 07/26/17

Version Number: 9.0

Page 4 of 17

Exclusion:

- Amenorrhea from other causes (Hyperandrogenemia and anovulation)
- Type 2 and Type 1 diabetes
- Medications: diabetes or diabetic drugs, estrogen/progestin therapy, antidepressants and antipsychotics, antiretroviral (HIV), oral steroids, weight loss drugs.
- ≤ 3 month washout of birth control pill (often prescribed for postmenopausal symptoms)
- Hysterectomy (partial or complete)
- Contraindications to estrogen treatment (unusual vaginal bleeding, blot clots, hepatic disease, bleeding disorder, past/present history of breast or uterine cancer, pregnant, breastfeeding)

Screening paradigm: Subjects will be recruited through endocrine and other medicine clinics at Tulane University Hospital & Clinic, Tulane-Lakeside Hospital and through referral from the Department of Medicine at Tulane Hospital & Clinic. Importantly, our recruitment efforts will be done with the Section of Reproductive Endocrinology and Infertility in the Department of Obstetrics and Gynecology at Tulane University Health Science Center. We will also use community advertisements and promotional materials (attached).

3. Procedure

Treatment plan: Subject will participate in a randomized scheme as follows:

- a) PLACEBO for 3 months (N=10 patients)
- b) BZA/CE for 3 months (N=10 patients)

BZA/CE group: Participants assigned to BZA/CE will receive a daily tablet containing conjugated estrogens 0.45 mg and bazedoxifene 20 mg. BZA/CE (bazedoxifene/conjugated estrogens) tablets, 0.45 mg/20 mg are oval, biconvex, pink tablets, branded with "0.45/20" in black ink on one side. The recommended and only FDA approved dosage is one BZA/CE tablet daily, taken without regard to meals ¹⁴. Tablets should be swallowed whole. If a dose of BZA/CE is missed, participants will be instructed to take it as soon as remembered unless it is almost time for the next scheduled dose. They should not take two doses at the same time. The dose is one tablet per day independent of weight and fat mass. Participants will be provided with information about BZA/CE and its potential side effects and contraindications. Pfizer will provide the medication.

PLACEBO group: In addition to receiving a placebo tablet (provided by Pfizer), participants assigned to the placebo group will be counseled on how to adapt to changes associated with menopause.

DEXA scans: will be performed using a Hologic QDR 4500A whole-body scanner. The scan takes about 5 – 15 minutes and the radiation dose is less than 1 mrem, equal to about 12-h of background radiation. The scans are analyzed with the QDR for Windows V11.1 software. In our hands, the SD is 320 g (CVs of 0.6%) and 300 g (CVs of 1.1%) for FFM and FM, respectively. We will also use the DXA data to estimate muscle mass.

Glucose and insulin: Fasting glucose and insulin will be measured after the 12-h overnight fast. Insulin levels will be collected at each time point during the IVGTT which is described below.

IV-Glucose Tolerance Test (IVGTT): The intravenous glucose tolerance test (IVGTT) interpreted with the minimal model provides individual indexes of insulin sensitivity (S_I) and glucose effectiveness (S_G).

Version Date: 07/26/17

Version Number: 9.0

Page **5** of **17**

Patients will have intravenous catheters inserted in a vein in each arm. One will be used for blood samples and the other to administer the IVGTT required medications - glucose and insulin. Baseline blood samples will be taken at -15, -10, and -1 min. before glucose is injected intravenously in the dose of 11.4 g/m² body surface area over 1 min. beginning at time 0. Blood samples will then be taken at timed intervals to check glucose levels via the YSI glucose Analyzer. Insulin will be administered intravenously over 30 seconds in the dose of 0.03 U/kg body weight twenty minutes after the glucose administration. Again, blood samples will be taken at timed intervals until the 3 hour IVGTT is completed. A total of 33 blood samples will be collected for both glucose and insulin according to the chart below.

Time (min)	Glucose and Insulin
-15	X
-5	X
-1	X
0	Glucose IV over 60 seconds – 11.4 g/m ² body surface area
+2	X
+3	X
+4	X
+5	X
+6	X
+8	X
+10	X
+12	X
+14	X
+16	X
+19	X
+20	Insulin iv over 30 seconds - -0.03 U/kg body weight
+22	X
+23	X

Version Date: 07/26/17

Version Number: 9.0

Page **6** of **17**

+24	X
+25	X
+27	X
+30	X
+35	X
+40	X
+50	X
+60	X
+70	X
+80	X
+90	X
+100	X
+120	X
+140	X
+160	X
+180	X

Biomarkers of Inflammation: We will measure serum cytokines (Leptin – Insulin – adiponectin – RBP4 - LCN2 – TNFa - IL6 – PAI-1 – FGF21) through high sensitivity ELISAs. These biomarkers will be collected prior to any testing at Visits 2 and 5 after a 12 hour fast.

Endothelial Function Test: This test will be done at Visits 2 and 5 after a 12 hour fast. It is a non-invasive test that uses Peripheral arterial tonometry (EndoPAT) to assess endothelial function.

Specifics of this Endothelial Function Test can be found in the “Addendum to BIM Study” document that is attached to this protocol.

4. Risks

Risks to Subjects: This Human Subjects Research meets the definition of a Clinical Trial.

Version Date: 07/26/17

Version Number: 9.0

Page 7 of 17

Sources of Materials

All data and specimens will be obtained solely for research purposes. These will include 1) detailed medical history, 2) physical exam including BMI and WHR measurement, 3) multiple blood samples to assess complete blood count, complete metabolic panel, lipid profile; glucose and insulin blood samples from IV-GTT testing, and cytokines(biomarkers of inflammation), 4) body composition measures by DXA (for details see section 3c. Approach), Endothelial Testing using the EndoPAT machine and 5) stored blood specimens used to study metabolic health and inflammation. All data from individual subjects will be maintained for confidentiality and names and identities will not be disclosed in any published document.

This study does not involve major risk to screeners and trial participants. To minimize the potential risks of the assessment methods and outcome variables, investigators will frequently monitor the study to assure that no volunteer suffers any adverse effects from participating in the research. Risks of complications will be reduced by carefully selecting participants for enrollment as per our inclusion/exclusion criteria. Other than participants being Overweight, with Obesity I and Obesity II at the time of enrollment, the inclusion and exclusion criteria were created to ensure women with low risk for bone fractures, have no diabetes and are not on medications such as diabetic drugs, dyslipidemia, estrogen/progestin therapy, antidepressants and antipsychotics. The Principal Investigator or its representative(s) will obtain medical clearance prior to each participant's enrollment.

Potential risks associated with the study procedures include:

- a) Analysis of archived of blood specimens: There is no risk for participants to have their blood collected and stored for future use pertaining to metabolic health and inflammation. All specimens will be de-identified and kept in a secure location.
- b) Blood pressure testing: Participants may experience temporary discomfort during blood pressure recordings due to the pressure of the cuff inflating on their arm.
- c) Blood draw: There is the possibility of pain and bruising at the vein on your arm where the needle is inserted. Multiple sticks may be necessary if there is difficulty in drawing participants blood. Aseptic (sterile) technique and trained personnel minimize these risks.
- d) Body composition assessment: The DXA scan involves extremely low levels radiation exposure. This technique has been demonstrated to be safe and approved for children. There are no known risks of the body scan
- e) IV Glucose Tolerance Test: The IV glucose tolerance test is the gold standard for assessing insulin sensitivity and secretion from the glucose and insulin dynamics observed during the IVGTT which are computerized as a minimal model using software. Some people feel nauseated or sweaty after receiving the glucose. Some people develop hypoglycemia. The IV(s) may be associated with pain or bruising where the needle(s) are inserted and the development of a bruise at these sites with a minimal possibility of infection. Trained personnel and aseptic (sterile) techniques are used to minimize these risks. The intended sites of catheterization will be cleaned thoroughly with an antiseptic and, after insertion; the area will be dressed so that it is not in contact with the outer environment. Also, the subject will be supervised, and all sites will be monitored for any signs of infection (increase in body temperature, swelling, redness, etc., around the insertion sites), upon which the catheter(s) will be removed immediately. Trained, credentialed personnel under the supervision of PIs will perform all procedures.
- f) Endothelial Function Test: The EndoPAT is performed with the participant in a lying or sitting position for approximately 15 minutes. The subject may become uncomfortable for that length of time. Finger probes are placed on each index finger and minimally inflated which may pose some discomfort to their fingertips. The finger probes are deflated after the testing is

Version Date: 07/26/17

Version Number: 9.0

Page **8** of **17**

completed. A cuff is placed on their non-dominant arm and inflated for about 5 minutes during the testing period. This may cause some discomfort and/or tingling in there arm, however it is considered very safe and should pass with the release of the cuff. Only Trained personnel will be performing this test.

Protection against Risks

Confidentiality

The study investigators will treat participant identity with professional standards of confidentiality. Each participant will be assigned an identification number and all participant protected health information/records/questionnaires/data will be coded and identified using these numbers rather than participant names. The coded participant list identifying participants by name will be stored separately from the number coded records/questionnaires/data. All participant records/data will be stored in locked file cabinets. Study results will be reported as group data and/or by participant identification number only. Study results may be presented in publications or at meetings/conferences, however participant identity will not be disclosed. A participant may request their personal health information or their personal study data/results at any time during the study and will be given copies.

All volunteers are assured of their confidentiality both verbally and in the informed consent form. The clinical facilities are strictly limited to the staff of the research institution and to research volunteers. This is accomplished by a variety of stringent security measures. All medical records are stored in locked areas. Access to these areas is limited to the clinical support staff, director of the clinical facilities, and the PIs. Electronic data storage is similarly restricted with only the PIs and authorized persons having access to databases containing confidential clinical records, i.e. those containing name OR other identifying information.

HIPPA Compliance

Tulane University Health Sciences Center complies with the federal 1996 Health Insurance Portability and Accountability Act (HIPPA). Specifically, Tulane University Health Sciences Center protects the privacy and confidentiality of medical records and information contained in medical records of persons who are subjects of research projects, including all Protected Health Information (PHI) as defined by the HIPAA Privacy Regulations. PHI of research subjects and the use or disclosure of such information is governed by PBRC research policies, as well as Common Rule, FDA regulations and other applicable laws.

Tulane University Health Sciences Center and the Principal Investigators (the persons chiefly responsible for the record) protect the privacy of research subjects and their PHI collected during a research project. Tulane University Health Sciences Center will not use or disclose existing PHI or PHI created during a research project, unless:

- The subject signs both (a) a HIPAA Authorization for use and disclosure of PHI using an approved Authorization Form or other form containing all the elements of legally effective HIPAA authorization and (b) the informed consent to participate in research form approved by the Institutional Review Board (IRB), or
- The IRB grants a waiver to the requirement of obtaining a signed HIPAA Authorization Form, or
- The IRB-approved protocol uses properly de-identified PHI

Version Date: 07/26/17

Version Number: 9.0

Page **9** of **17**

- The IRB-approved protocol uses the limited data set and the Principal Investigator signs a limited data use agreement with the entity that maintains the designated record set.

5. Benefits

We cannot promise benefits from participating in this study but we expect clear improvements of metabolic health for all the women randomized to pharmacological interventions. The results of the study will provide important information about pharmacological intervention with BZA/CE that may help in controlling weight/fat gain in women during early post menopause. This information can contribute to the development of evidence-based recommendations to help manage weight during menopause.

6. Remuneration

Subjects will receive compensation for their time and travel in the form of a Clincard. They will receive \$25.00 for study visits 1, 3, and 4 and \$50.00 for study visits 2 and 5. The Clincard is a reloadable debit/credit card that will be given to each subject upon completion of their first visit. After each completed study visit thereafter, the card will be uploaded with the amount allowed for that visit. The subject will received compensation for each completed study visit. If they complete all study visits, they will receive up to a total of \$175.00. If a subject is withdrawn from the study by either the investigator or sponsor, or withdraws voluntarily, the subject will be compensated only for the study visits they complete.

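### Does the promise of fed glucose and insulin in aim (b) leave an endpoint with no measurement behind it?

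*Combined protocol and SAP*

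**What the plan says.** Section 1 sets the endpoints to be measured "at the beginning of the study and after 3 months of treatment". Under aim (b), the rationale is that in mice "TSEC treatment decreases fasting and fed blood glucose levels", and the Design sentence commits the trial to the treatment effect "on fasting and fed glucose and insulin levels".

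Section 3, under Glucose and insulin, gives two sources of data. First, "Fasting glucose and insulin will be measured after the 12-h overnight fast". Second, "Insulin levels will be collected at each time point during the IVGTT which is described below". The IVGTT is introduced in aim (c) as the test "which will be studied using the minimal model", with the insulin sensitivity index, the acute insulin response (AIRg) and DI as its outputs. Glucose goes in intravenously at time 0 and insulin is injected "twenty minutes after the glucose administration".

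The Biomarkers of Inflammation paragraph lists a panel that includes insulin and states: "These biomarkers will be collected prior to any testing at Visits 2 and 5 after a 12 hour fast". The specimen list in section 4 (Sources of Materials) adds a complete metabolic panel, without stating a visit or a fasting condition.

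**The concern.** A named endpoint should have a sample, a time and a definition behind it. In the available text, fed glucose and fed insulin have none. The word also seems deliberate, because the mouse rationale for the same aim uses it.

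If no fed sample is taken, half of the quantities in aim (b) cannot be reported. If IVGTT values are meant to stand in, the plan names no time point or summary. The fed result would then rest on a choice made after the data exist and tested at p < 0.05. Most post-glucose draws also follow an insulin injection, so a fed insulin value taken from them would partly reflect the injected dose.

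A lesser doubt concerns the IVGTT schedule itself. The text and the chart disagree on the number of samples and on one basal time.

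**Working it through.** No power or sample-size figure bears on this point. The check compares what aim (b) promises with what the procedures collect, and counts the IVGTT chart.

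**Promise against procedure**

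| Quantity in aim (b) | Described measurement in the available text |
|---|---|
| Fasting glucose | Yes, section 3, after the overnight fast |
| Fasting insulin | Yes, section 3; also in the fasting biomarker panel |
| Fed glucose | None named; IVGTT post-glucose values exist |
| Fed insulin | None named; IVGTT post-glucose values exist |

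That is 2 of 4 without a named measurement.

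**IVGTT chart (section 3)**

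- Before glucose: -15, -5, -1 min, which is 3 draws.
- After glucose and before the +20 min insulin: +2, 3, 4, 5, 6, 8, 10, 12, 14, 16, 19, which is 11 draws.
- After the insulin: +22, 23, 24, 25, 27, 30, 35, 40, 50, 60, 70, 80, 90, 100, 120, 140, 160, 180, which is 18 draws.
- Total: 3 + 11 + 18 = 32, against a stated total of 33.
- Post-glucose draws: 11 + 18 = 29, of which 18/29 = 62% follow injected insulin and 11/29 = 38% do not.

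**Three readings and their consequences**

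1. *The fed measurement is described in the part not available for review.* Some text between section 6 (Remuneration) and the later references was not available. Payments show five visits, but the available text gives content only for screening and for Visits 2 and 5. On this reading there is no gap.
2. *IVGTT values are meant.* The Glucose and insulin paragraph places IVGTT insulin beside the fasting values, and the chart collects both analytes. Data exist and only a definition is missing. AIRg, already named in aim (c), summarises first-phase insulin release, and 11 draws precede the injection.
3. *The word was carried over from the mouse rationale.* The hypothesis and the expectation in aim (b) speak only of glucose and insulin levels, without *fed*. The mouse rationale mentions fed glucose but not fed insulin. On this reading nothing fed is collected, and the report says so.

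Fasting glucose, fasting insulin, Si and DI are the same under all three.

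**The schedule mismatch**

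The text gives -15, -10 and -1 min for the basal draws; the chart gives -15, -5 and -1. A chart with both -10 and -5 would hold 32 + 1 = 33 draws, the stated total, but the text would still omit -5. That explanation is a guess. Both disputed times precede the glucose injection, and nothing in the documents shows that Si or DI depends on which is used.

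**The case for a change.** The strongest case for a change is that the commitment is explicit and the IVGTT does not honour it as written. Intravenous glucose is not a meal, aim (c) gives the IVGTT its own outputs, and an undefined outcome invites choosing a favourable time point. A dated line of wording would cost almost nothing.

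Much of this stands. The documents never say that an IVGTT value is the fed value, and an IVGTT response should not be presented as fed without explanation. A positive fed claim chosen from 29 time points would deserve little weight.

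The possible remedies gain little, however. Adding a fed draw is a new procedure and could not be recovered for women already assessed. The planned end was September 2015 and this version is dated 26 July 2017, although the documents do not say how many women had been assessed. Naming one IVGTT value would define a response to intravenous glucose, which is still not the fed state. Deleting the word alters no result.

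Nor can the risk from an open choice be sized from the documents. They give no correlation between candidate definitions, no variance and no number of candidates, so any error rate would follow from assumptions and would apply equally to any trial of this size.

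**Conclusion.** The observation is correct on the available text: two of the four quantities in aim (b) have no described fed measurement and no named IVGTT substitute. It does not call for a change. This is a pilot whose only statement about detectable effects (section 1, Statistical Methods) concerns Si and DI, and those, with fasting glucose and insulin, remain sound if the plan is followed as written. The gap is one that an analyst fills sensibly by labelling any post-glucose value as a response to intravenous glucose, or by reporting that no fed value was measured.

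The 33 against 32 count and the -10 against -5 min basal time are clerical inconsistencies between text and chart. The two should agree, but no effect on Si or DI has been shown.

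This conclusion rests on two conditions: that the part of the document not available for review does not make the fed values a principal outcome, and that no claim of a fed effect is later drawn from a selected IVGTT time point.
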